Intravesical (bladder) electrical stimulation This procedure is specific to participants in the bladder stimulation arm. A sterile stimulation catheter (Gaeltec custom catheter, 7-French) will be placed in the bladder through the urethra and the electrode contacts will be positioned to be floating within the bladder. The electrode contacts will be surrounded by ~30 ml of saline infused through the catheter. Impedance measurements will be recorded to monitor electrode integrity. A single return electrode will also be placed on the abdominal skin above the pubic bone. Stimuli will be delivered as 0.2 ms charge-balanced biphasic rectangular current pulses applied between the catheter electrode and the return surface electrode. Stimulation frequency will be set at 20 Hz and amplitude will be adjusted individually to 80% of the maximum tolerable intensity (Jiang and Lindstrom 1999, Gladh et al. 2003). Participants will be instructed to inform the study staff of any unpleasant sensations they may experience and may elect to terminate stimulation at any point. Electrical stimulation will be applied to bladder sensory nerves for up to 60 minutes prior to the start of urodynamic studies (Gladh et al. 2003, Deng et al. 2017).

Intraurethral electrical stimulation This procedure is specific to participants in the urethral stimulation arm. A sterile stimulation catheter (Gaeltec custom catheter, 7-French) will be placed in the urethra and positioned with the electrode contact 10-14 mm from the bladder neck to stimulate the proximal urethral sensory nerves. The catheter and electrode leads will be secured to the participant's leg with medical tape. Impedance measurements will be recorded to monitor electrode integrity. A single return electrode will also be placed on the abdominal skin above the pubic bone. Stimuli will be delivered as 0.2 ms charge-balanced biphasic rectangular current pulses applied between the catheter electrode and the neutral surface electrode. Stimulation frequency will be 10 Hz (may switch 2 or 20 Hz in subsequent participants if unresponsive) and amplitude will be adjusted individually to 80% of the maximum tolerable intensity (Gustafson et al. 2004, Yoo et al. 2011). Electrical stimulation will be applied to urethral sensory nerves at "strong desire to void" during cystometry. The participant will then be given permission to void at

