"maximum cystometric capacity" with continuous intraurethral stimulation. Participants will be instructed to inform the study staff of any unpleasant sensations they may experience and may elect to terminate stimulation and participation at any point.

Cystometry After bladder stimulation or during intraurethral stimulation, standard urodynamics will be performed to assess bladder sensation and storage. Residual urine volume in the bladder will be removed by catheterization prior to cystometry. A dual-chamber 8-French catheter will be passed through the urethra into the bladder for retrograde filling. A second 8-French catheter will be placed in the vagina to measure intra-abdominal pressure. A stimulation electrode catheter will only be inserted in the intraurethral stimulation arm per the above methods. EMG pads will then be placed at 3 and 9 o'clock on each side of the perineum in an area not obstructed by hair or skin folds. These pads each have adhesive, which allows them to adhere in place through the study. Both the urethral and vaginal catheters will be zeroed to atmospheric pressure. The bladder will then be filled with room-temperature sterile saline solution in a retrograde fashion using a pump. Bladder sensation and urgency will be assessed while filling. Bladder pressure will be continuously observed and recorded during the study for evidence of involuntary detrusor contractions. The following values will be recorded from this portion of the study: volume of first sensation during bladder filling, first desire to void, strong desire to void, maximum cystometric capacity, presence or absence of detrusor overactivity.

Pressure-flow study A standard pressure flow study will be performed to evaluate voiding function after stimulation. The transurethral and intra-vaginal catheters are left in place after cystometry and the participant will be asked to void around them, into a commode. Bladder and abdominal pressures will be recorded, as well as urine flow over time. Variables that will be recorded in this portion of the study include the following: voided volume, postvoid residual volume, pressure at maximum flow, flow time, abdominal pressure during voiding, interrupted versus continuous flow, and pelvic floor muscle activity during micturition (as determined by EMG activity).

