Uroflowmetry This standard procedure may be performed if participants are unable to void past the catheters in pressure flow studies. The dual chamber bladder catheter will be removed, and the participant will be instructed to void while sitting on a commode chair. A postvoid residual volume will be measured by straight catheterization. Variables that will be recorded include the following: voided volume, postvoid residual volume, flow rate, flow quality, and voided percentage. While this test sacrifices our secondary study objectives, we will still be able to fulfill our primary objectives of improved sensation and improved voiding function if the participant can void without catheters.

Selection of Subjects

• List inclusion/exclusion criteria and how subjects will be identified.

Inclusion Criteria:

- Females ages 18 and older
- Able to provide informed consent and agree to the study risks
- Willing to withdraw from medications affecting urination for the 48 hours prior to the procedure (e.g., alpha-adrenergic antagonists, cholinergic agonists, cholinesterase inhibitors)
- Has the below response to 2 of the 3 bulleted questions:
 - Questions regarding self-reported poor sensation during bladder filling or emptying (one or more of the below)

Question: In the past 7 days, where did you feel sensations when you felt you needed to urinate? Answer: "No" response for Bladder Area

Question: In the past 7 days, how often did you have no sensation of urine flow while you were urinating?

Answer: "Most of the time" or "Every time" response

Question: In the past 7 days, how often did you feel that your bladder was not completely empty after urination?

Answer: "Most of the time" or "Every time" response

Questions regarding self-reported bothersome urinary symptoms (one or more of the below)

Question: In the past 7 days, how satisfied were you with your bladder function? Answer: "Not at all satisfied" or "Somewhat satisfied" response

Question: In the past 7 days, how bothered were you by urinary symptoms?

Answer: "Very bothered" or "Extremely bothered" response

 Standard uroflowmetry with a voiding efficiency (voided volume / voided volume + residual volume) of < 80%, voided volume + residual volume must be >150ml for measurement

Exclusion Criteria:

- Preexisting neurological impairment (e.g., spinal cord injury, multiple sclerosis, Guillain-Barre, cauda equina syndrome, cerebrovascular accident, Parkinson's disease, traumatic brain injury)

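### In the urethral arm, the fallback void accepted for Primary Aim 1 may take place with the current off, and the plan neither settles nor records whether it does

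*Combined protocol and SAP*

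**What the plan says.** All places are in the combined protocol and SAP.

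- **Intraurethral electrical stimulation.** The start of current is tied to a reported sensation: "Electrical stimulation will be applied to urethral sensory nerves at 'strong desire to void' during cystometry". The woman then voids at capacity "with continuous intraurethral stimulation". Current passes between a 7-French urethral catheter electrode and a skin electrode.
- **Cystometry.** The electrode catheter is specific to this arm: "A stimulation electrode catheter will only be inserted in the intraurethral stimulation arm per the above methods". It is in addition to an 8-French dual-chamber catheter in the urethra. This section places urodynamics after bladder stimulation but during urethral stimulation.
- **Pressure-flow study and Study procedure visit.** Both describe the urodynamic tests as following stimulation, with no distinction by arm.
- **Uroflowmetry.** The fallback is introduced with "This standard procedure may be performed if participants are unable to void past the catheters in pressure flow studies". Only the dual-chamber bladder catheter is named as removed. The section concedes that the secondary objectives are lost, then adds "we will still be able to fulfill our primary objectives of improved sensation and improved voiding function if the participant can void without catheters". It does not separate the arms.
- **Statistical Methods.** Primary Aim 1 compares voided percentage by Wilcoxon signed-rank test. No analysis set, minimum exposure or rule for unstimulated voids is given.

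**The concern.** In the urethral arm the intervention is current acting while the woman voids. In the bladder arm stimulation is finished before urodynamics begin, so catheter removal does not change what was delivered. The fallback rule treats both arms alike. For a urethral-arm woman, a void with no catheter in place cannot be a void under urethral current.

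The fallback is foreseeable. These women are recruited partly for poor emptying, and in this arm two catheters lie in the urethra during the pressure-flow void. The Devices paragraph itself links a thinner catheter to easier voiding.

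If such voids enter Primary Aim 1 as stimulated, two errors are possible, in opposite directions. A real effect of stimulation during voiding is diluted, or better emptying after catheter removal is read as an effect of stimulation. Neither the pressure-flow nor the uroflowmetry variable list includes current status or on-time, so these voids could not be identified afterwards from the listed data.

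**Working it through.** **1. The sections side by side, urethral arm**

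| Question | Intraurethral stimulation / Cystometry | Pressure-flow / Study procedure visit | Uroflowmetry |
|---|---|---|---|
| Current on during the counted void? | Yes, continuous | Wording places the test after stimulation | Not stated |
| Electrode catheter in place? | Yes | Not stated separately | Not named as removed, but the void is described as catheter-free |
| Void counts for the primary objective? | – | Yes (Primary Aim 1) | Yes, either arm |

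There are two readings of the fallback. If the electrode is out, the void is unstimulated and does not meet the definition of the intervention. If the electrode stays in, the catheter-free description is wrong. Either way the text needs correcting.

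**2. The plan's own power figure**

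Inputs from Data Analysis & Statistical Considerations: n = 20, dz = 0.67, power 0.8, detectable change 7.5% in voided percentage (taken here as percentage points). Alpha and sidedness are not stated; two-sided 0.05 is assumed.

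- Implied SD of the paired difference: 7.5 / 0.67 = 11.2 points.
- Noncentrality: 0.67 × √20 = 3.00. Paired t-test power: 0.811.
- Exact Wilcoxon signed-rank, normal differences, 20,000 simulated trials: 0.789.

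The stated 0.8 is reproduced, with almost no slack.

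**3. Illustration of dilution, all 20 women**

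Suppose k women are analysed as stimulated but have zero mean effect, and the rest have dz = 0.67. The average dz is 0.67 × (20 − k)/20. Power is by exact Wilcoxon simulation.

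| k | Average dz | Power, k women kept | Power, k women left out |
|---|---|---|---|
| 0 | 0.670 | 0.79 | – |
| 1 | 0.637 | 0.74 | 0.76 |
| 2 | 0.603 | 0.70 | 0.74 |
| 4 | 0.536 | 0.58 | 0.67 |

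The last column assumes that being left out is unrelated to voiding ability, which is doubtful here. It does not argue for exclusion.

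**4. Illustration within the arm**

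Arm size is not fixed, because allocation follows current perception threshold; assume 10 women. Borrow 7.5 points as the true gain, although the plan gives it as the detectable change for the whole sample.

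- 2 voids with no effect: 7.5 × 8/10 = 6.0 points.
- 3 voids with no effect: 7.5 × 7/10 = 5.25 points.
- Power in an arm of 10 at dz = 0.67: 0.46 with none affected, 0.30 with two.

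In the other direction, suppose stimulation does nothing and catheter removal adds g points in 2 of 10 women. The arm mean becomes 0.2 × g. To imitate a mean gain of 7.5, g would have to be 7.5 / 0.2 = 37.5 points. The documents give no value for g. Such a gain arises only if the paired baseline void was made with catheters in place.

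**The case against.** The strongest reply is that fallback women were treated. Uroflowmetry follows cystometry and a failed pressure-flow attempt, so a woman who reported strong desire had current from that point through the attempt. That is correct. A reader might infer that she is counted as stimulated at zero dose, but the documents do not support this. What may be missing is current during the void that is measured. Even that is not certain, because the electrode catheter is not named as removed. The reply narrows the point to a conflict in the text; it does not resolve the conflict.

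The references to testing after stimulation may be generic wording that fits the bladder arm. That is plausible, and the Cystometry section does distinguish the arms. The wording still needs aligning.

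A reader might also infer that the entry criteria select women who will never report strong desire. They do not. Poor sensation is one of three criteria of which two suffice, and the bladder-area answer is one of three alternatives within it. That question asks where the need to urinate was felt, not whether it was felt. Allocation also sends women whose bladder threshold deviates more to the bladder arm. No figure suggests how often strong desire would be absent, and nothing says such a woman is counted as stimulated. She would also receive some current while the amplitude is titrated. What stands is an omission: the text does not say how she is handled.

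Nor does the fallback contaminate Secondary Aim 3, since the Uroflowmetry section says the secondary objectives are sacrificed.

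Finally, restricting the analysis to current-on voids would drop women because they could not void around catheters, which is close to selecting on the outcome. This stands, and it shapes the fix.

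**Conclusion.** The point holds for Primary Aim 1 in the urethral arm. The intervention is defined as voiding under continuous current, while the fallback accepts a catheter-free void and leaves electrode and current status open. Following the text, a void without stimulation can be credited to intraurethral stimulation. The absent start rule is a smaller, related gap. The bladder arm is not affected.

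The size is unknown, because the documents give no rate of fallback voids or of absent strong desire. The figures above rest on assumed counts, an assumed alpha, and zero effect in affected women. The last may be too pessimistic, since current during the failed attempt could carry over. They show only that a trial of 20 with about 0.79 power has little room: one or two such women matter. The direction of the bias cannot be settled from the documents.

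This should be corrected before analysis. It does not invalidate the design.

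**What to change.** 1. **Reconcile the text.** The Study procedure visit, Intraurethral electrical stimulation, Cystometry, Pressure-flow study and Uroflowmetry sections should agree on whether the electrode and current remain during the fallback void. The sponsor should also state how a woman who never reports strong desire is handled. Which clinical rule applies is for the sponsor and investigators; none is proposed here.
2. **Record exposure.** For the void that is counted, record current on or off, and on-time.
3. **Prespecify the Primary Aim 1 analysis.** Keep all women allocated to the urethral arm in the main summary. Flag current-off voids and report them separately. Add a sensitivity analysis restricted to current-on voids, with the stated caveat that the restriction may select on voiding ability.
4. **Limit the claim.** Do not present a current-off void as evidence that stimulation during voiding works.

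The cost is a short amendment and an exposure entry on the case report form. The on-stimulation estimate will be less precise, because it may rest on fewer women.

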Official Title: AMPLIFY: Amplifying Sensation in Underactive Bladder

Protocol#: Pro00106457 Version 1.17

NCT#: NCT04516434

Document Date: 04/10/2024

Standard Research Summary

Purpose of the Study

Objectives & hypotheses to be tested

The overall objective of this study is to improve lower urinary tract symptoms (LUTS) in adult neurologically-intact women with underactive bladder through electrical stimulation of bladder sensory nerves or urethral sensory nerves. The first primary endpoints are that sensory nerve fiber stimulation to the bladder will decrease bothersome urinary symptoms during filling and emptying, stimulation to the urethra will decrease bothersome urinary symptoms during emptying, and that bladder stimulation will increase bladder sensation during filling and emptying, as determined by our lower urinary tract symptom questionnaire. The second primary endpoint is that sensory nerve fiber stimulation to the bladder or urethra will increase bladder emptying during pressure-flow studies in participants with poor baseline bladder function. In addition to these primary endpoints, we will also observe secondary endpoints that will be compared to paired baseline measurements. Secondary endpoints include (a) increased bladder or urethral current perception threshold relative to normative data, (b) decreased bladder volumes at cystometric endpoints with intravesical (bladder) electrical stimulation, and (c) increased detrusor contraction strength and contraction duration with intraurethral electrical stimulation.

Background & Significance

• Should support the scientific aims of the research

The storage and elimination of urine is regulated by neural circuits in the brain and spinal cord to coordinate function between the urinary bladder and the urethra (Fowler et al. 2008). During micturition (bladder emptying), the elimination of urine is facilitated by bladder muscle (detrusor) contraction and urethral and pelvic floor muscle relaxation. Urine flow through the urethra also activates sensory nerves to amplify bladder contractions and maintain efficient bladder emptying (Jung et al. 1999, Bump 2000). Incomplete emptying and urinary retention occur when these mechanisms are disrupted or poorly coordinated.

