Study procedure visit: Participants will be reminded by phone call or email 48 hours before the study visit to withdraw from medications affecting urination per our inclusion criteria. On the day of the visit, participants will sign and date the informed consent document and complete a compensation form, LURN SI-29 questionnaire survey, and demographics questionnaire survey. Pre-procedure vital signs, point of care urinalysis, and a pregnancy test will be obtained. Participants will be excluded with a positive pregnancy test or delayed until resolution of infection with a positive urinalysis (per exclusion criteria). If participants have negative urinalysis, negative pregnancy test, and meet inclusion/exclusion criteria they will undergo current perception threshold (CPT) testing in the bladder and urethra.

Participants will be assigned to the intervention arm based on CPT. CPT data will be analyzed immediately by percentage change against normative data to stratify investigational allocation to intravesical (bladder) electrical stimulation or intraurethral electrical stimulation (Kenton et al. 2007). The allocation will be as follows: 1) if percentage change of urethral CPT > percentage change of bladder CPT then participants will receive intraurethral electrical stimulation, 2) if percentage change of bladder CPT > percentage change of

urethral CPT then participants will receive intravesical electrical stimulation, or 3) if percentage change of urethral CPT = percentage change of bladder CPT then participants will receive intravesical stimulation when cystometry "first desire to void" > 275ml or intraurethral stimulation when pressure-flow detrusor pressure at maximum flow < 30 cmH2O and maximum flow < 10 ml/s. After the investigational session of stimulation, participants will undergo post-study urodynamic studies which will include cystometry and pressure-flow studies. At the completion of these procedures, participants will be given standard urogynecology post urodynamic study instructions. They will also be instructed to complete remotely a post-study condition LURN SI-29 questionnaire that will be emailed via RedCap 7 days after the study visit. At that time, they will be considered to have completed the study.

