- There is a risk of painful sensations from electrical stimulation to the bladder and urethra. Participants can elect to decrease or terminate stimulation at any point during the study. We will minimize the risk of activating nerve fibers carrying painful stimuli by individually adjusting current amplitude to 80% of their maximum tolerable intensity. Every subject will be titrated down from a stimulation parameter that they feel is uncomfortable. The stimulation amplitude will be guided by the values obtained from the Current Perception Threshold forced choice paradigm, where a baseline intensity alignment automatically increases amplitude until the participant reports detection. Participants will be informed of any sensations they may perceive as unpleasant and may elect to terminate stimulation at any point.
- Participating in this study while pregnant may expose the unborn child to unknown risks. There is no risk level because we have excluded pregnant women.

- There may be some unknown and unforeseeable risks related to the study. Participants will be informed of any significant new information learned during the study that might cause them to change their mind about participating in the study. Significant new findings developed during the research, which may relate to their willingness to participate will also be provided to them.

Costs to the Subject

• Describe and justify any costs that the subject will incur as a result of participation; ordinarily, subjects should not be expected to pay for research without receiving direct benefit.

There will be no cost to the subject as a result of the participation.

Data Analysis & Statistical Considerations

Describe endpoints and power calculations. Provide a detailed description of how study data will be
analyzed, including statistical methods used, and how ineligible subjects will be handled and which
subjects will be included for analysis. Include planned sample size justification. Provide estimated time
to target accrual and accrual rate. Describe interim analysis including plans to stop accrual during
monitoring. Phase I studies, include dose escalation schema and criteria for dose escalation with
definition of MTD and DLT.

Expected enrollment n = 20 neurologically-intact women with underactive bladder **Expected effect size** (dz) = 0.67 **Power (1 – \beta) =** 0.8

Time to Target Accrual 2 years

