To account for participants failing to meet our eligibility criteria, it is anticipated that a total of 100 adult women will be screened to achieve n=20 total study participants. We expect to screen all patients with ICD codes suggestive of underactive bladder because a DEDUCE query revealed that in 2019 Duke Urogynecology clinics saw 34 patients meeting our criteria and approximately 10 of those patients went on for urodynamic studies. It is our expectation that the lack of consistent terminology and diagnostic parameters for underactive bladder will result in a large patient population failing to meet our eligibility criteria. Our expected enrollment will enable detection of a 7.5% change in voided percentage after stimulation with power (1-beta) of 0.8.

Statistical Methods

Primary Aim 1: Use of intraurethral electrical stimulation or intravesical electrical stimulation to assess increase in voided percentage during pressure-flow studies

Hypothesis: Electrical stimulation will increase voided percentage, and this hypothesis will be evaluated with non-parametric tests.

Method: Data will be analyzed by Wilcoxon signed-rank test to determine the influence of intravesical and intraurethral stimulation on bladder emptying.

Primary Aim 2: Use of LURN SI-29 questionnaire to assess whether electrical stimulation decreases urinary bothersome symptoms and increase bladder sensation during filling and emptying

Hypothesis: Intravesical (bladder) stimulation will decrease affirmatory responses to bothersome urinary symptoms and increase affirmatory responses to sensation during filling and emptying, whereas intraurethral stimulation will decrease affirmatory responses to bothersome symptoms during emptying.

Method: Data will be analyzed by the McNemar Exact Test or the Wilcoxon signed-rank test to determine the influence of intravesical or intraurethral stimulation on sensation.

Secondary Aim 1: Assess bladder or urethral current perception threshold (CPT) in women with underactive bladders

Hypothesis: Women with underactive bladder will have increased bladder CPT and increased urethral CPT (reduced sensory nerve activity) compared to normative data in asymptomatic women, and this hypothesis will be evaluated with the Dunn's multiple comparisons test.

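### Does Primary Aim 2 need a pooled test in all 20 women ahead of the arm-by-arm tests to keep the stated 80% power?

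*Combined protocol and SAP*

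**What the plan says.** The objectives make one claim per site among the first primary endpoints: "sensory nerve fiber stimulation to the bladder will decrease bothersome urinary symptoms during filling and emptying", and "stimulation to the urethra will decrease bothersome urinary symptoms during emptying". Increased sensation is claimed for bladder stimulation only.

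Under Statistical Methods, the Primary Aim 2 heading asks about electrical stimulation in general. The hypothesis then separates the sites: after the bladder-stimulation claims it continues "whereas intraurethral stimulation will decrease affirmatory responses to bothersome symptoms during emptying". The method is the "McNemar Exact Test or the Wilcoxon signed-rank test to determine the influence of intravesical or intraurethral stimulation on sensation". For Primary Aim 1 (voided percentage) the method is a signed-rank test "to determine the influence of intravesical and intraurethral stimulation on bladder emptying".

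Arm sizes are not fixed: "Participants will be assigned to the intervention arm based on CPT" (Design & Procedures, Study procedure visit). The sample-size basis, under Data Analysis & Statistical Considerations, is "Expected enrollment n = 20 neurologically-intact women with underactive bladder", with dz 0.67 and power 0.8. The endpoint to which that power belongs is named: "Our expected enrollment will enable detection of a 7.5% change in voided percentage after stimulation with power (1-beta) of 0.8". Neither an alpha level nor a power for the questionnaire is given.

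**The concern.** Less bother during emptying is predicted at both sites, so every woman could contribute to that claim. Yet the hypothesis states it once per site, and the method sentence joins the sites with *or*, where the Aim 1 method has *and*. Read that way, the analyst would test two arms of unplanned size, while the only power figure in the document fits a single test on 20 women.

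Two things would be at stake. Each arm would have roughly half the advertised power or less. And if both sites worked equally well, the likeliest result would be one arm significant and the other not, which a reader could mistake for a difference between bladder and urethral stimulation. Two unadjusted tests would also carry about a 9.5% chance of at least one false claim. A pooled test first, followed by the arms only if it succeeds, looks like a cheap cure.

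**Working it through.** **Inputs.** From Data Analysis & Statistical Considerations: n = 20, dz = 0.67, power 0.8, for a 7.5% change in voided percentage. Assumed, because the document does not say: two-sided 0.05, normally distributed paired differences, a 10/10 split, and the same dz for a LURN emptying-bother score as for voided percentage.

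**1. The plan's own figure.** For a paired t-test, the noncentrality is dz × √n = 0.67 × √20 = 3.00, on 19 degrees of freedom with critical value 2.093. Power is 0.81. The exact signed-rank test, simulated, gives 0.79. So the stated 0.8 reproduces with all 20 women in one test at two-sided 0.05. At one-sided 0.05, 16 women would be enough, though no split of 20 gives both arms 16.

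**2. By arm, at the same dz (exact signed-rank).**

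| Women in arm | 6 | 8 | 10 | 12 | 14 | 20 |
|---|---|---|---|---|---|---|
| Power | 18% | 32% | 46% | 51% | 62% | 79% |

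The arms are independent, so at 10/10, with 0.456 per arm:
- both pass: 0.456² = 0.21
- exactly one passes: 2 × 0.456 × 0.544 = 0.50
- neither passes: 0.544² = 0.30

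The arithmetic behind the worry is correct.

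**3. Whether a stated power is lost.** The power sentence names voided percentage. Nothing in the document gives dz, power or a detectable change for the LURN SI-29. The 79% for a pooled LURN test is borrowed from another endpoint. With McNemar's exact test, the other named option, pooled power at n = 20 would be 32% if 30% of women improved and 5% worsened, and 79% at 50% and 5%. A shortfall against 80% cannot be charged to Aim 2, which never claimed it.

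**4. Whether the text orders a split.** *Or* against *and* does not settle it, because the Aim 1 heading also joins the two sites with *or*, and Aim 1 is the endpoint taken to be pooled. The Aim 2 heading speaks of electrical stimulation overall. The Aim 2 method sentence ends on sensation, which is predicted for bladder stimulation only. Only the hypothesis is clearly by site.

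**5. What a pooled-first rule would change.** The arms are tested only after a significant pooled test.

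| True dz (bladder, urethra or the reverse), split | Result | Arms tested directly | Pooled test first |
|---|---|---|---|
| 0.67 and 0.67, 10/10 | exactly one arm passes | 50% | 45% |
| 0.67 and 0.67, 14/6 | exactly one arm passes | 58% | 55% |
| 0.67 and 0.25, 10/10 | better arm passes | 46% | 32% |
| 0.67 and 0, 10/10 | working arm passes | 46% | 19% |

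The 45% in the first row is any arm 66% minus both arms 21%. So the feared one-arm result falls by only 3 to 5 points. Once the pooled test has succeeded at 10/10, exactly one arm passes in 0.45 / 0.79 = 57% of trials.

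**6. Whether equal effects can be presumed.** Under Design & Procedures, bladder stimulation is given for up to an hour before urodynamics at 20 Hz. Urethral stimulation starts late in filling and runs through voiding at 10 Hz, with provision to change frequency. CPT results sort women between the two. These are different interventions in differently selected women, so the lower rows of the table are realistic.

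**The case for a change.** The best case for the concern is this. The hypothesis is by site, no pooled LURN test or order of testing is written down, and the plan itself predicts an emptying benefit at both sites. A pooled test of that shared prediction would then have 79% power, against 46% per arm. At 10/10 it beats a single arm once the other arm's dz exceeds about 0.25. The ordered procedure is valid: it brings the chance of any false arm claim, when neither site works, from about 9.5% to 2.9%, and costs little if both work (44% per arm instead of 46%). An arm of five or fewer women could not reach two-sided 0.05 at all (smallest p = 2 × 0.5⁵ = 0.0625).

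Those figures stand. They show that a pooled lead claim is a reasonable option, and that by-arm results from this study will be imprecise. They do not show that the plan is wrong. The pooled test asks whether CPT-guided stimulation as a strategy helps, whereas the hypotheses ask what each site does. It would also need an emptying-specific bother score, which the plan does not define; the bother question shown under Selection of Subjects is about urinary symptoms in general. Very small arms stay just as small under either approach. It would help readers to have it written down whether Aim 2 is pooled or by arm, but that is missing detail and not an error.

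**Conclusion.** The concern does not hold. The calculations are right, at 46% per arm of 10 against 79% pooled, given dz 0.67, two-sided 0.05 and the carry-over of dz to the questionnaire. But the 80% was stated for voided percentage alone, so Aim 2 forfeits no stated power, and its wording is ambiguous about pooling. A pooled-first order would leave the one-arm result almost as frequent (45% against 50% at 10/10, 55% against 58% at 14/6), and would cut a single working arm's power from 46% to 19%, or to 32% if the other arm's dz is 0.25. Which order is better depends on how alike the two sites' effects are, and the document gives no basis for assuming that they are equal. In a study that calls itself a pilot and states site-specific hypotheses, testing by site is an acceptable choice on which statisticians may differ.
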